- 14) Optional at selected sites and only for subjects who had skin biopsies taken in the parent trial LP0162-1325.

Abbreviations: CDLQI = Children's Dermatology Life Quality Index; ECG = electrocardiogram; ePRO = electronic patient-reported outcome; DLQI = Dermatology Life Quality Index; IMP = investigational medicinal product; NA = not applicable; NRS = numeric rating scale.

Date: 21-Feb-2022 Version: 14.0
Page 31 of 187

Panel 4: ECZTEND - schedule of trial procedures (Week 64–EOT) until end of May 2021

			Tr	eatment	t period	1		SFU ¹			
Visits	14 20	15 21	16 22	17 23	18	19	EOT visit	SFU visit	Unscheduled visit (if applicable) ³	Early termination (if applicable) ¹	References (protocol section)
Weeks	64 112	72 120	80 128	88 136	96	104	Variable ² (max 140)	Variable ²			
Visit window (days) ⁴	±3	±3	±3	±3	±3	±3	±3	±3			
Treatments											
Concomitant medication and concurrent procedures	X	X	X	X	X	X	X	X	X	X	9.6
Tralokinumab administration/dispensing ⁵	X	X	X	X	X	X			X		9.2, 9.8.3
Treatment compliance	X	X	X	X	X	X	X		X	X	9.8.4
Investigator assessments of efficacy											
Investigator's Global Assessment	X	X	X	X	X	X	X		X	X	11.3.1.1
Eczema Area and Severity Index	X	X	X	X	X	X	X		X	X	11.3.1.2
SCORing Atopic Dermatitis	X	X	X	X	X	X	X		X	X	11.3.1.3
Investigator assessments of safety											
Weight						X	X			X	11.4.1
Vital signs	X	X	X	X	X	X	X	X	X	X	11.4.2
Physical examination			X			X	X	X	X	X	11.4.3
Electrocardiogram			X			X	X	X	X	X	11.4.4
Chemistry, haematology, immunoglobulin E			X			X	X	X	X	X	11.4.5
Urinalysis ⁶			X			X	X	X	X	X	11.4.5
Urine pregnancy test	X	X	X	X	X	X	X	X	X	X	11.4.5

Trial ID: LP0162-1337

THIS DOCUMENT CONTAINS CONFIDENTIAL INFORMATION AND MUST NOT BE COPIED OR MADE AVAILABLE TO ANY THIRD PARTY WITHOUT THE PRIOR WRITTEN CONSENT OF THE LEO PHARMA GROUP

			Tr	eatmen	t period	1		SFU ¹	Unscheduled		References	
Visits	14 20	15 21	16 22	17 23	18	19	EOT visit	SFU visit	visit (if applicable) ³	Early termination (if applicable) ¹	(protocol section)	
Weeks	64 112	72 120	80 128	88 136	96	104	Variable ² (max 140)	Variable ²				
Visit window (days) ⁴	±3	±3	±3	±3	±3	±3	±3	±3				
Investigator assessments of safety (continued)												
Anti-drug antibodies			X			X	X	X	X	X	11.4.6	
Pharmacokinetics blood sample			X			X	X	X	X	X	11.5	
Adverse events	X	X	X	X	X	X	X	X	X	X	13	
Patient-reported outcomes												
Patient Oriented Eczema Measure			X			X	X		X	X	11.3.2.1	
Dermatology Life Quality Index (DLQI)/CDLQI ⁷			X			X	X		X	X	11.3.2.2	

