EuroQoL 5-Dimension Health Questionnaire 5-Level ⁸			X			X	X		X	X	11.3.2.3	
Worst Weekly Pruritus numeric rating scale ⁹ Eczema-related Sleep numeric rating scale ⁹ Patient use of topical treatment ¹⁰	X	X	X	X	X	X	X		X	Х	11.3.2.4	

- 1) Subjects who withdraw from the trial will be followed up as described in Section 10. The final safety follow-up visit will be 16 weeks after the last dose (i.e. 14 weeks after the EOT visit).
- 2) The number of weeks until the EOT visit (2 weeks after the last dose of tralokinumab, maximum 140 weeks) and SFU visit (maximum 154 weeks) for each subject will depend on the time of their trial entry and treatment duration.
- 3) Assessments and procedures to be performed at an unscheduled visit are at the discretion of the investigator. If the unscheduled visit involves administration of rescue treatment, the investigator should make every attempt to conduct efficacy and safety assessments (at least disease severity scores [IGA and EASI], concomitant medications/procedures, and AEs) immediately before administering any rescue treatment (see Section 9.5).
- 4) If the date of a trial visit does not conform to the clinical trial protocol, subsequent visits should be planned to maintain the visit schedule relative to baseline.

Trial ID: LP0162-1337

5) At trial visits, tralokinumab will be injected at the trial site, preferably by the subject or their caregiver, alternatively by site staff. At each trial visit, subjects will be provided with tralokinumab to be administered at home until the next trial visit. In case of intercurrent illness that may compromise the safety of the subject, or fever within 72 hours prior to administration, tralokinumab administration should be rescheduled. If an anaphylactic reaction occurs, blood samples should be drawn for the analysis of serum tryptase (see details in Section 9.2).

- 6) Urine samples will be tested at the trial site (dipstick). In case of abnormal dipstick results, a urine sample will be sent to the central laboratory for microscopic examination (leucocytes, erythrocytes, and casts) (Section 11.4.5).
- 7) Adult subjects from all parent trials, except the LP0162-1334 trial, will perform the DLQI. Subjects from the parent trial LP0162-1334 will perform the CDLQI, independent of the age of the subject during participation in ECZTEND.
- 8) Subjects from the parent trial LP0162-1334 will not perform the EuroQoL 5-Dimension Health Questionnaire 5-Level.

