Weeks since first treatment in LP0162- 1337	-2	0	2	4	8	16	24	32 64 96 128 160 192 224 256	40 72 104 136 168 200 232 264	48 80 112 144 176 208 240	56 88 120 152 184 216 248	Variable ² (max 268)	SFU visit Variable ²	Un- scheduled visit (if applicable) ³	Early termination (if applicable) ¹	References (protocol section)
Visit type	Site	Site	Site	Site	Site	Site	Site	Tele- phone ⁴	Short Site	Tele- phone ⁴	Standard Site	Site	Site			
Visit window (days) ⁵	-3	NA	±3	±3	±3	±3	±3	±3	±3	±3	±3	±3	±3			
Patient-reported	d outcom	es (cont	inued)													
Worst Weekly Pruritus numeric rating scale Eczema-related																
Sleep numeric rating scale	X	X	X	X	X	X	X		X		X	X		X	X	11.3.2.4
Patient use of topical treatment ¹⁴																

- 1) If screening/baseline visits are performed on the same day as visit(s) in the parent trial, the order of assessments should be adhered to, working in parallel for both protocols. Assessments where data are captured in different vendor systems databases (ECG, ePRO, and laboratory tests) need to be completed twice. In such cases, the parent trial assessment should be performed first, followed by the trial LP0162-1337 assessment. For subjects included in the trial prior to protocol version 10, the first visit after May 2021 can be a site visit or a telephone visit.
- 2) Subjects who withdraw from the trial will be followed up as described in Section 10. The final safety follow-up visit will be 4 weeks after the last dose (i.e. 2 weeks after the EOT visit). For subjects from the parent trial LP0162-1334, the maximum number of weeks until the EOT visit will be 114 weeks.
- 3) Assessments and procedures to be performed at an unscheduled visit are at the discretion of the investigator. If the unscheduled visit involves administration of rescue treatment, the investigator should make every attempt to conduct efficacy and safety assessments (at least disease severity scores [IGA and EASI], concomitant medications/procedures, and AEs) immediately before administering any rescue treatment (see Section 9.5).

Trial ID: LP0162-1337

THIS DOCUMENT CONTAINS CONFIDENTIAL INFORMATION AND MUST NOT BE COPIED OR MADE AVAILABLE TO ANY THIRD PARTY WITHOUT THE PRIOR WRITTEN CONSENT OF THE LEO PHARMA GROUP

- 4) For subjects from the parent trial LP0162-1334, the telephone visit should preferably be performed as a video call.

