7.1.4 Safety follow-up period (after last IMP dose)

All subjects will complete an off-treatment follow-up period for the assessment of safety, PK, and ADA.

The timing of the safety follow-up visit depends on the parent trial and on whether the subject has consented to participate after May 2021, as summarised in Panel 8.

Panel 8: Safety follow-up visit

Parent trial	Subject did NOT consent to continue after May 2021	Subject DID re-consent or consent to participate after May 2021
LP0162-1325, -1326, -1334 (adolescents), -1339, -1341, -1342, -1343, -1346, and TRA-WEI-0015-I	16 weeks after last dose	4 weeks after last dose

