5.8.4 Clinical laboratory evaluation

Clinical laboratory evaluations will be tabulated as described in the CTP Section 14.3.8.3. However, only presenting summaries of the total, tralokinumab naïve, re-treated, and continuously treated, not the washed-out subjects.

Additionally, shift tables will be produced for relevant laboratory tests showing categories at baseline against highest or lowest test measurement in the treatment period (see Panel 4).

Panel 4: Clinical laboratory test where shift tables will be prepared for lowest/highest	
measurement in the treatment period	

Clinical laboratory test	Shift table to lowest	Shift table to highest		
Chemistry				
Sodium	Yes	Yes		
Potassium	Yes	Yes		
Creatinine	-	Yes		
Calcium	Yes	Yes		
Alkaline phosphatase	-	Yes		
Aspartate aminotransferase	-	Yes		
Alanine aminotransferase	-	Yes		
Bilirubin	-	Yes		
Cholesterol	-	Yes		
LDL cholesterol	-	Yes		
HDL cholesterol	Yes	Yes		

Clinical laboratory test	Shift table to lowest	Shift table to highest
Triglycerides	-	Yes
Glucose (non-fasting)	Yes	Yes
Hematology		
Hemoglobin	Yes	Yes
Neutrophils, segmented	Yes	-
Lymphocytes	Yes	Yes
Monocytes	Yes	Yes
Eosinophils	-	Yes
Basophils	-	Yes
Platelets	Yes	Yes

Abbreviations: HDL = high density lipoprotein; LDL = low density lipoprotein; - = not applicable.

Laboratory values will be considered potentially clinically significant if satisfying the PCS criteria specified in the ADRG. All post-baseline measurements (including samples from unscheduled visits) will be included in the search for PCS values. For haematology and chemistry laboratory parameters, the number and percentage of subjects with at least one post-baseline PCS value will be summarised with the denominator being all subjects with at least one post-baseline assessment. All PCS values will be included in the listings.

Subjects fulfilling Hy's law will be presented.

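### One percentage for potentially clinically significant (PCS) laboratory and vital-sign values pools the off-treatment safety follow-up visit with the treatment period

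*SAP*

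**What the plan says.** SAP 5.8.4 sets the search rule: "All post-baseline measurements (including samples from unscheduled visits) will be included in the search for PCS values". It reports the number and percentage of subjects with at least one such value, "with the denominator being all subjects with at least one post-baseline assessment". SAP 5.8.2 uses the same rule and denominator for vital signs. On thresholds, 5.8.4 says "Laboratory values will be considered potentially clinically significant if satisfying the PCS criteria specified in the ADRG"; the ADRG (analysis data reviewer's guide) is not among the documents. Neither section gives the search an end date or SFU values a separate line.

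The follow-up visit supplies values that fall under this rule. Protocol 7.1.4 states: "All subjects will complete an off-treatment follow-up period for the assessment of safety, PK, and ADA". Panel 4 (schedule until end of May 2021) and Panel 5 (schedule after May 2021) both mark vital signs and the row "Chemistry, haematology, immunoglobulin E" in the SFU column. The timing differs by cohort:

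- Subjects who did not continue after May 2021: "The final safety follow-up visit will be 16 weeks after the last dose (i.e. 14 weeks after the EOT visit").
- Subjects who consented to take part after May 2021: "The final safety follow-up visit will be 4 weeks after the last dose (i.e. 2 weeks after the EOT visit").

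Other safety outputs separate the periods. The additional shift tables in 5.8.4 compare "categories at baseline against highest or lowest test measurement in the treatment period". SAP 5.8.1 presents adverse events for the treatment and SFU periods and uses the safety follow-up analysis set of SAP section 4 for the latter. The primary endpoint (SAP 5.5) is confined to the treatment period.

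**The concern.** A subject whose first PCS value appears at the SFU visit is counted in the same cell as one whose value appeared during dosing. A reader of a long-term treatment trial may take that percentage as describing the treatment period, and nothing in the two sections says how much of it comes from follow-up.

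The SFU visit also differs from the treatment visits. Dosing has stopped, the gap since the last dose is 16 weeks in one cohort and 4 in the other, and some restrictions on other atopic dermatitis therapy end with treatment (Protocol 9.7). One SFU sample also weighs more for a subject with few on-treatment samples. At stake is the interpretation of a descriptive safety percentage. No test or endpoint depends on it.

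**Working it through.** The documents state no PCS percentage, so there is no figure to reproduce. The check counts scheduled samples and asks how much one SFU sample can add.

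**Scheduled post-baseline on-treatment samples (m)**

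- Laboratory, Panels 3 and 4, longest: Weeks 8, 16, 32, 56, 80, 104, 128 and end of treatment (EOT), so m = 8. SFU is 1 of 9.
- Laboratory, Panel 5 visits counted from Week 0, longest: Weeks 8, 16, 56, 88, 120, 152, 184, 216, 248 and EOT, so m = 10. SFU is 1 of 11.
- Laboratory, about half a year of treatment: Weeks 8, 16 and EOT, so m = 3. SFU is 1 of 4.
- Vital signs, Panels 3 and 4, longest: Weeks 2, 4, 8, 12, 16, 32, 56, then every 8 weeks from 64 to 136, and EOT. That is 7 + 10 + 1, so m = 18. SFU is 1 of 19.
- Vital signs, Panel 5, longest: Weeks 2, 4, 8, 16, eight short site visits, seven standard site visits and EOT. That is 4 + 8 + 7 + 1, so m = 20. SFU is 1 of 21.

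Subjects who moved from one schedule to the other have a mixture. For laboratory tests the mixture never has fewer on-treatment samples than Panel 5 alone, so the bound for them is no larger.

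**Effect of one SFU sample**

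Assume each sample has PCS probability p, independently, with the same p on and off treatment.

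- Treatment period only: 1 − (1 − p)^m
- With SFU: 1 − (1 − p)^(m+1)
- Relative rise: p(1 − p)^m / [1 − (1 − p)^m], which approaches its maximum 1/m as p becomes small.

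The value of p is an assumption; the range shown is 0.1% to 5%.

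| Case | m | Maximum relative rise (1/m) | p = 1%: treatment period → pooled | Absolute rise, p = 0.1% to 5% |
|---|---|---|---|---|
| Laboratory, Panels 3/4 longest | 8 | 12.5% | 7.73% → 8.65% | 0.10 to 3.32 points |
| Laboratory, Panel 5 longest | 10 | 10% | 9.56% → 10.47% | 0.10 to 2.99 points |
| Laboratory, about half a year | 3 | 33% | 2.97% → 3.94% | 0.10 to 4.29 points |
| Vital signs, Panels 3/4 longest | 18 | 5.6% | 16.55% → 17.38% | 0.10 to 1.99 points |
| Vital signs, Panel 5 longest | 20 | 5% | 18.21% → 19.03% | 0.10 to 1.79 points |

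**Direction**

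For a subject who already has an on-treatment sample, an SFU value can only add to the numerator. A subject whose only post-baseline sample is the SFU one also enters the denominator. With assumed numbers, 32/1,580 = 2.03% on treatment becomes 32/1,600 = 2.00% if 20 such subjects join and none is a PCS case. A fall is therefore possible.

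**Exposure at the SFU visit**

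SAP 7.1 and Protocol 8.2 equate 16 weeks with 5 half-lives, so the half-life is 16/5 = 3.2 weeks. Taking simple exponential decline from the level at the last dose:

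- 16 weeks: 2^(−16/3.2) = 0.031, about 3% remaining.
- 4 weeks: 2^(−4/3.2) = 0.42, about 42% remaining.

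**The case against.** The strongest reply is that the SAP defines a post-baseline percentage with a matching post-baseline denominator and never calls it on-treatment. An inclusive search is a legitimate safety choice in a single-arm trial with no testing, and PCS is not an endpoint. The treatment-emergent definition for adverse events is likewise open-ended. By-visit summaries and the PCS listings let a reader trace follow-up values. The ADRG, not supplied, might also set a window.

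Most of this stands, and it rules out several stronger readings that a reader might infer:

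- That the percentage is inflated or biased. It is a declared quantity, its direction against an on-treatment figure is likely but not guaranteed, and no PCS rate is available to size it.
- That all SFU values are off-drug. This fits the 16-week visit. At 4 weeks subjects are off dosing but still exposed, and an abnormal value could still be drug-related.
- That PCS is the leading laboratory result, or that the PCS and shift tables contradict each other. The SAP adds PCS to the protocol's tabulations. Shift tables use reference-range categories and PCS uses its own criteria, so the two could differ even with identical windows.
- That relapse of atopic dermatitis drives PCS values at follow-up. Nothing in the documents says so.

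What the reply does not remove is that one stated rule pools the two periods without giving a reason, while adverse events get separate SFU tables despite their open-ended definition. The SAP cites the ADRG for PCS criteria and sets the search window itself.

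**Conclusion.** The point holds as a modest improvement in reporting. As written, SAP 5.8.2 and 5.8.4 combine treatment-period and SFU values in one PCS percentage, unlike the worst-value shift tables and the adverse event tables. Compared with an on-treatment percentage, the result is likely to be higher, by at most about 10–12.5% in relative terms for laboratory tests and 5–6% for vital signs on the longest schedules, and by up to about 33% for laboratory tests with about half a year of treatment.

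These bounds rest on independent samples and equal PCS rates on and off treatment. If the same subjects tend to have repeated PCS values, the rise is smaller; if the rate is higher at follow-up, it could be larger. The documents do not establish a biased safety conclusion.

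**What to change.** In SAP 5.8.2 and 5.8.4, report PCS values for the treatment period, defined as first ECZTEND dose through the EOT or early termination visit and including unscheduled on-treatment samples. Limit the denominator to subjects with at least one measurement in that window. Report PCS values at the SFU visit in a separate row, using the safety follow-up analysis set already defined in SAP section 4. Keep all PCS values in the listings.

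The cost is a sentence in each section, one date filter and one extra row per parameter. No data are lost.

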	Known primary immunodeficiency disorder.								
Investigational medicinal product	Name/active substance: tralokinumab (human recombinant IL-13 monoclonal antibody of the immunoglobulin G4 subclass that specifically binds to human IL-13 and blocks interaction with the IL-13 receptors).								
	 Dosage form: solution (in accessorised pre-filled syringe, 1.0 mL fill volume). 								
	• Concentration: 150 mg/mL.								
	 Dose for adult subjects from all parent trials, except the parent trial LP0162-1334: 600 mg initial loading dose, then 300 mg every second week. 								
	• Dose for subjects from the parent trial LP0162-1334*: 300 mg every second week.								
	*All subjects from the parent trial LP0162-1334, independent of the subject's age when included in ECZTEND.								
	Method of administration: subcutaneous injection.								
Duration of treatment	The duration of the treatment period for each subject will depend on when the subject enters the trial after completing the parent trial, and by which treatment stop date they have consented to (end of May 2021, end of May 2022, or a country-specific end of treatment day):								
	• For subjects who did NOT re-consent to participate in the trial after May 2021, trial treatment was stopped by end of May 2021. Treatment duration was maximum 140 weeks.								
	• For subjects from the parent trial LP0162-1334 who consented to participate in the trial after May 2021, trial treatment will be stopped by end of May 2022. Treatment duration will be maximum 114 weeks.								
	• For subjects from the parent trials LP0162-1325, -1326, -1339, -1341, -1342, -1343, -1346, and TRA-WEI-0015-I who consent to participate in the trial after May 2021, trial treatment will be stopped at a country-specific treatment completion date. Treatment duration will be maximum 268 weeks.								
Number of subjects	It is assumed that approximately 1,600 subjects will be assigned to treatment.								
Number and distribution of trial sites	Approximately 330 sites in Canada, Europe, Japan, and the US.								
Statistical methods	Primary endpoint AEs will be summarised for all treated subjects (full analysis set) and will be presented by Medical Dictionary for Regulatory Activities (MedDRA) preferred term and primary system organ class (SOC) as percentage of subjects with AEs, number of AEs, and rate of AEs (number of AEs per 100 patient-years of exposure).								

Page 22 of 187

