7.1 Overall trial design

7.1.1 Overview

This is an open-label phase 3 trial to study the long-term safety of tralokinumab administered to adult subjects (≥18 years) and adolescent subjects (12 to <18 years) with AD who participated in previous trials with tralokinumab. The trial will include a screening period of 2 weeks (Week -2 to Week 0), which is expected to overlap with the last period in the parent trial for the majority of subjects, and a long-term treatment period of approximately 0.5 years to up to 5 years. The duration of the treatment period for each subject will depend on when they enter the trial after completing the parent trial, and by which treatment stop date they have consented to (end of May 2021, end of May 2022, or a country-specific end of treatment day according to Appendix 3J).

The visit schedule until May 2021 is different from the visit schedule after May 2021, where a number of site visits were replaced by mandatory telephone visits to reduce the burden of frequent site visits (Panel 2 and Panel 5).

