1.2 Trial design

Panel 2: Trial design

- **Notes:** Subjects were included in ECZTEND after completion of the treatment period in the parent trial, and continued with a long-term treatment period of approximately 0.5 to 5 years in ECZTEND. Subjects who did NOT re-consent to participation in the trial after May 2021 stopped IMP treatment by end of May 2021 followed by 16 weeks of SFU (top row visit schedule). * Subjects from the parent trial LP0162-1334 did not perform the EQ-5D-5L. ** Visit schedule after May 2021 applied to subjects who consented to continue in the trial after May 2021, or who were included in the trial after May 2021. Treatment ended at a country-specific treatment end date, or by end of May 2022 (subjects from the parent trial LP0162-1334).
- Abbreviations: ADA = anti-drug antibodies; CDLQI = Children's Dermatology Life Quality Index;
 DLQI = Dermatology Life Quality Index; EASI = Eczema Area and Severity Index; EQ-5D-5L = EuroQoL 5 Dimension Health Questionnaire 5-Level; IGA = Investigator's Global Assessment; IMP = investigational medicinal product; PK = pharmacokinetics; POEM = Patient Oriented Eczema Measure; Q2W = every second week; SCORAD = Scoring Atopic Dermatitis; SFU = safety follow-up; TCS = topical corticosteroids; w = weeks.

Protocol amendments

The following CTP amendments significantly affected data interpretation, analyzed populations, or statistical analyses:

- Amendment 2 (31-Aug-2018):
 - Allowed subjects from parent trial LP0162-1346 to enter ECZTEND.
 - Changed the timeframe of the primary endpoint from "up to Week 128" to "last treatment visit".

- Amendment 6 (17-Feb-2020):
 - Changed the timeframe of the primary endpoint from "last treatment visit" to "up to Week 142".
 - Allowed adolescent subjects from parent trial LP0162-1334 to enter ECZTEND including associated assessments and precautions.
 - Increased estimated sample size to 1500 subjects.
- Amendment 7 (25-Nov-2020):
 - Updated the visit schedule after May 2021, extending the trial up to 5 years.
 - Converted every other site visit after Week 24 to telephone visits.
 - Allowed subjects from parent trial LP0162-1343 and TRA-WEI-0015-I to enter ECZTEND.
 - Added country specific end of treatment dates.
 - Updates to all endpoints in accordance with the extension of the trial and update to the schedule of assessments.

For a complete overview of all changes introduced in protocol amendments, see the CTP Appendix 8.

2 Testing strategy

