5.8.2 Vital signs

Vital signs will be tabulated as described in the CTP Section 14.3.8.2. However, only presenting summaries of the total, tralokinumab naïve, re-treated, and continuously treated, not the washed-out subjects.

Additionally, vital sign values will be considered potentially clinically significant if satisfying the PCS criteria specified in the ADRG. All post-baseline measurements (including samples from unscheduled visits) will be included in the search for PCS values. Number and percentage of subjects with at least one post-baseline PCS value will be summarised with the denominator being all subjects with at least one post-baseline assessment. All PCS values will be included in the listings.

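### PCS laboratory values and vital signs are summarised only as a crude ever-percentage, which depends strongly on follow-up length and number of tests and, as written, does not set aside subjects already PCS at baseline

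*SAP*

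**What the plan says.** SAP 5.8.4 plans that, for haematology and chemistry, "the number and percentage of subjects with at least one post-baseline PCS value will be summarised with the denominator being all subjects" who have at least one post-baseline assessment. SAP 5.8.2 has the same rule for vital signs: "Number and percentage of subjects with at least one post-baseline PCS value will be summarised with the denominator being all subjects", with the same restriction.

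On what is searched, SAP 5.8.4 says: "All post-baseline measurements (including samples from unscheduled visits) will be included in the search for PCS values". SAP 5.8.2 repeats this. A value qualifies "if satisfying the PCS criteria specified in the ADRG"; that guide is not among the documents.

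Neither section gives person-time, a time to first PCS, a fixed time window, or a rule for subjects who are PCS at baseline.

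Protocol 7.1.1 describes "a long-term treatment period of approximately 0.5 years to up to 5 years". The Protocol synopsis gives maxima of 114, 140 or 268 weeks, depending on parent trial and consent.

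Elsewhere the SAP does bring in time. Section 5.8.1 gives adverse events (AEs) a first-event incidence rate per 100 patient-years at risk. Section 5.4.1 uses the Aalen-Johansen estimator for withdrawal.

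**The concern.** The share of subjects who ever have a qualifying value is not a measure of risk when subjects are watched for very different lengths of time. A PCS value can be found only when a sample or reading is taken, so the share also depends on how often subjects are tested. Unscheduled samples add to this, and Protocol 11.4.5.3 requires repeats of clinically significant abnormal laboratory results.

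Two readings are at stake. One is the total PCS percentage, which cannot sensibly be set beside a source with different follow-up. The other is any comparison of naïve, re-treated and continuously treated subjects, if their follow-up differs. Separately, a subject who meets the threshold at ECZTEND baseline and again later counts the same as a subject with a new abnormality.

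**Working it through.** The documents give no PCS percentage or rate, so there is no planned figure to reproduce. The rates below are assumptions and show only how the statistic behaves.

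**1. Scheduled post-baseline tests (Protocol Panels 3 to 5)**
- Laboratory, 26 weeks: Weeks 8 and 16, end of treatment (EOT), safety follow-up (SFU) = 4.
- Laboratory, 140 weeks, Panels 3 and 4: Weeks 8, 16, 32, 56, 80, 104, 128, EOT, SFU = 9.
- Laboratory, 268 weeks, Panel 5 alone: Weeks 8, 16, 56, 88, 120, 152, 184, 216, 248, EOT, SFU = 11.
- Laboratory, 268 weeks, switching schedule in May 2021: Weeks 8, 16, 32, 56, 80, 104, 120, 152, 184, 216, 248, EOT, SFU = about 13.
- Vital signs, Panel 5: 6 at 26 weeks and 21 at 268 weeks. A subject who switched schedules would have more than 21.

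**2. Repeat testing alone.** The ever-percentage with k independent tests is 1 − (1 − p)^k.

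| k | p = 0.5% | p = 1% | p = 2% |
|---|---|---|---|
| 4 (laboratory, 26 weeks) | 2.0% | 3.9% | 7.8% |
| 11 (laboratory, 268 weeks) | 5.4% | 10.5% | 19.9% |
| 13 (laboratory, 268 weeks, switched) | 6.3% | 12.2% | 23.1% |
| 6 (vital signs, 26 weeks) | 3.0% | 5.9% | 11.4% |
| 21 (vital signs, 268 weeks) | 10.0% | 19.0% | 34.6% |

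Correlation within a subject would reduce this growth, not remove it.

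**3. A constant rate per year instead.** The ever-percentage is 1 − exp(−rate × t). At 2 per 100 patient-years it is 1.0% at 0.5 years and 9.5% at 5 years. For rates of 1 to 5 per 100 patient-years, the 5-year figure is 9.0 to 9.8 times the 0.5-year figure. For scale, at 2 per 100 patient-years, 2 years gives 3.9% and 3.5 years gives 6.8%; doubling the rate at 2 years gives 7.7%.

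**4. Baseline PCS.** If a share b is PCS at baseline and all of these meet the criterion again, the percentage is b + (1 − b)(1 − exp(−rate × t)). With b = 2% and 2 per 100 patient-years, 1.0% becomes 3.0% at 0.5 years, and 9.5% becomes 11.3% at 5 years.

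**5. Would one overall rate per 100 patient-years solve it?** Not under the per-test model, because laboratory testing is denser early. At 1% per test, counting person-time to first PCS or end of treatment:
- 26 weeks: 2.97 / 0.493 = 6.0 per 100 patient-years without the SFU sample, and 3.94 / 0.493 = 8.0 with it.
- 268 weeks: from 9.56 / 4.889 = 2.0 (Panel 5, no SFU sample) to 12.25 / 4.816 = 2.5 (switched, with SFU sample).

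The bias reverses: with identical risk per test, long follow-up looks better. The rate is stable only if the hazard is constant per year.

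**The case against.** The strongest reply is that the PCS table is one screen among several:
- Clinically significant abnormal laboratory or vital-sign findings after screening must be reported as AEs (Protocol 13.2), and AEs do get person-time rates.
- Laboratory values have shift tables from baseline category to end of treatment (Protocol 14.3.8.3) and, for the Panel 4 tests, to the highest or lowest value on treatment (SAP 5.8.4).
- Changes from baseline are tabulated by visit, all PCS values are listed, and exclusion criterion 28 can keep out subjects with abnormal screening findings.

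This stands in part. PCS thresholds and investigator judgement overlap but are not the same. The shift tables use low, normal and high rather than PCS limits, and the highest/lowest version also grows with follow-up. Vital signs have no shift table. Criterion 28 rests on judgement.

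A reader might go further and infer that the PCS percentages reflect follow-up more than drug effect. The documents do not support that: they give no PCS rates, and in a single-arm, open-label trial no PCS summary isolates a drug effect. A reader might also infer that the naïve, re-treated and continuous groups will be distorted. SAP 7.1 defines them by prior treatment and dosing gap, and no follow-up by group is given, so this is a risk only. Nor is it certain that baseline-abnormal subjects are counted, because the ADRG criteria may include a change from baseline.

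**Conclusion.** The point holds in limited form. As planned, the PCS percentages depend strongly on follow-up length and number of tests. At an assumed 1% per independent test, scheduled testing alone moves the laboratory figure from 3.9% to between 10.5% and 12.2%, and the vital-sign figure from 5.9% to 19.0%, between 26 and 268 weeks. As written they also include subjects already PCS at ECZTEND baseline, subject to the unseen ADRG.

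The effect is confined to the interpretation of descriptive safety tables. SAP section 2 specifies no testing, and the primary endpoint is the number of AEs. The change is still worth making, because long-term safety is the primary objective and the SAP already contains the methods needed.

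**What to change.** In SAP 5.8.2 and 5.8.4:
- Keep the crude n (%), but split it into subjects not PCS at ECZTEND baseline and subjects already PCS at baseline.
- For those not PCS at baseline, add the cumulative incidence of first PCS at fixed times, for example Weeks 16, 56, 104, 152, 216 and 264, using the Aalen-Johansen estimator already in SAP 5.4.1. State which endings of follow-up are censoring and which are competing events.
- State whether SFU samples count. All post-baseline measurements can include them, 4 or 16 weeks after the last dose, whereas the Panel 4 shift tables are limited to the treatment period.
- If a rate per 100 patient-years is also shown, give it by period, because an overall rate would favour long follow-up.

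Fixed times remove the follow-up problem but not all of the testing-frequency problem. By Week 56 there are 4 scheduled laboratory tests under Panel 3 (Weeks 8, 16, 32, 56) and 3 under Panel 5 (Weeks 8, 16, 56), or 3.9% against 3.0% at 1% per test. A footnote should say so.

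The cost is a few more tables and slightly smaller denominators. No new data are needed.
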